Cover page

Official title:

Modelling propofol pharmacokinetics and pharmacodynamics during an intravenous anaesthesia guided by the bispectral index (BIS)

NCT number:

NCT02713698

Date of the document:

08/01/2016

Study protocol and statistical analysis plan

Anaesthetic protocol

Preoperative evaluation

- Assessment of past medical history, allergies and current medications;
- Physical exam (vital signals, weight, height) and airway assessment with Mallampati score, dentition, range of neck motion and thyromental distance;
- Laboratory tests confirmation when necessary;
- Frailty quantitative clinical evaluation Clinical Frailty Scale;
- Single-frequency bioelectrical impedance analysis;
- Presentation and discussion of informed consent elements;
- Participant information leaflet delivery.

Anaesthetic technique

- Intra-operative monitoring: continuous pulse oximetry, electrocardiography, invasive blood pressure, neuromuscular blockade (*train-of-four* pattern) and bilateral BIS (BIS VISTATM Bilateral Monitoring System, Covidien, Colorado, US);
- Remifentanil effect-site concentration set at 3 ng/mL (Minto's model), using a target controlled infusion device (Orchestra® Base Primea – Fresenius Kabi) and arterial line placement;
- Induction of general anaesthesia: remifentanil effect-site concentration set at 3 ng/mL, rocuronium 0.6 mg/kg and propofol at 2000 mg/h until LOC, defined by "loss of eyelash reflex" and "loss of response to name calling";
- At LOC, propofol infusion rate will be adjusted to 6 mL/kg/h and orotracheal intubation will be accomplished when TOF count 0-1 and BIS 40-60;
- Time to LOC in seconds and total dose of propofol in mg will be recorded;
- Maintenance of general anaesthesia: remifentanil effect-site target will be adjusted by 0,5 ng/mL changes according to physiologic parameters, propofol will be altered by 5 mg/mL changes targeting the BIS values between 40 and 60 and rocuronium 0.1 mg/kg in order to maintain TOF count ≤ 2;

- Maintenance fluid requirements follow estimated by the 4-2-1 rule: 4 mL/kg/h for the first 10 kg, 2 mL/kg/h for the second 10 kg and 1 mL/kg/h for every kg above 20 kg;
- Parameters of mechanical ventilation: volume-controlled mode, tidal volume 6-8
 mL/kg, PEEP (positive end-expiratory pressure) 5 mmHg and FiO₂ 40-50%;
- Thirty min before the end of surgery intravenous paracetamol 1000 mg, parecoxibe 40 mg and tramadol 100 mg will be administered;

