- Postoperative nausea and vomiting prophylaxis with dexamethasone 4 mg in the beginning of surgery and ondansetron 4 mg thirty min before the end of surgery;
- At the end of surgery, propofol and remifentanil infusions will be discontinued and neostigmine 2.5 mg and atropine 1 mg or sugammadex 2 mg/kg will be administered to reversal neuromuscular blockade;
- Extubation will be performed after an adequate reversal of neuromuscular blockade (TOF ratio ≥ 90%) considering consciousness recovery and respiratory mechanics adequacy;
- Arterial blood samples will be obtained after arterial line placement, immediately
 after LOC, immediately before surgery and after every 20-30 min during propofol
 infusion. After stopping propofol infusion, arterial blood samples will be acquired
 every 10 min until recovery of consciousness. The maximum blood sample per patient
 will be 20 mL;
- Total dose of propofol and total dose of remifentanil, total time of propofol and remifentanil infusion and the time until consciousness recovery after propofol discontinuation will be recorded.

Post-operative evaluation

 Application of modified Brice protocol in the recovery room and in the first 24-48 h after the surgery.

*With respect to patients submitted to an orthopaedic surgery, the anaesthetic protocol will be slightly different considering the standard practice in the hospital. When indicated, a peripheral nerve block will be executed and the opioid of choice will be fentanyl instead of remifentanil. When possible, a laryngeal mask airway will be used.

Quantification of serum propofol concentration

The quantification of propofol in plasma will be performed using gas chromatography/ion trap-mass spectrometry (GC/IT-MS).

Arterial blood samples are collected into serum tubes and centrifuged at 4000 rpm for 5 min in order to obtain plasma. Serum is preserved at -80 °C until analysis.

Extraction procedure is performed by the addition of 50 μ L of thymol (0.01 mg/mL) and 1mL of ultra-pure water to a 0.5 mL aliquot of serum and to the propofol calibration standards. To each processed sample 0.5 mL of burate buffer (pH=9) is added and mixed by inversion for 5 min. Then, 300 μ L of chloroform:ethylacetate (70:30 v:v) is added and also mixed by inversion for 20 min. After a 10 min centrifugation, 2 μ L of the organic phase is injected into the GC/IT-MS injector.

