The identification of propofol in each sample is performed in the same chromatographic conditions, by comparative analysis between the retention times of pure compounds with the compounds in the injected samples. Blank samples are obtained from propofol-free plasma, which were requested to the Clinical Haematology Service of CHP. All the plasma donors received both written and oral information regarding the study and they signed informed consent.

Statistical analysis: PKPD Modeling Analysis

A conventional 3-compartment, first-order elimination, PK model will be used to fit propofol data. Parameter estimates will be obtained using a nonlinear mixed effects model with the program NONMEM.

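### Does the plan have to fix in advance how body size, frailty and the orthopaedic regimen enter the propofol model?

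*Combined protocol and SAP*

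**What the plan says.** Under Statistical analysis: PKPD Modeling Analysis the combined document states "A conventional 3-compartment, first-order elimination, PK model will be used to fit propofol data" and then "Parameter estimates will be obtained using a nonlinear mixed effects model with the program NONMEM". Nothing else follows. There is no size descriptor, covariate list, selection criterion or PD model, and no mention of orthopaedic patients.

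Preoperative evaluation lists "Physical exam (vital signals, weight, height" among the examination items, then "Frailty quantitative clinical evaluation Clinical Frailty Scale" and "Single-frequency bioelectrical impedance analysis".

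Anaesthetic technique begins with "Remifentanil effect-site concentration set at 3 ng/mL", delivered by target-controlled infusion. On data capture it says "Time to LOC in seconds and total dose of propofol in mg will be recorded". A later item adds the total doses and infusion times of propofol and remifentanil, and the time to recovery.

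The note at the end of Post-operative evaluation sets out a variant for orthopaedic surgery: "When indicated, a peripheral nerve block will be executed and the opioid of choice will be fentanyl instead of remifentanil". A laryngeal mask replaces the tube where feasible.

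The document gives no sample size, significance level, hypothesis or expected share of orthopaedic patients.

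**The concern.** Frailty and bioimpedance have no stated use other than, presumably, the model. Weight has other uses, in per-kilogram dosing, fluids and tidal volume. If the size and frailty data are meant as covariates, the order in which they enter affects the result. Frailty tested without size can absorb a weight effect. Frailty tested after weight can absorb a body-composition effect that fat-free mass would have explained. Frailty tried on every parameter invites a chance finding. A reader of the final report could then not tell a planned frailty result from a selected one.

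On the PD side, the title and the section heading both promise PD modelling, and opioid regimen is an obvious candidate to shift the relation between propofol concentration and BIS. Opioid exposure is expressed only as a remifentanil effect-site concentration, which has no value in a patient given fentanyl. It is also unclear whether the words about indication govern the block alone or the opioid too. The recorded items do not name fentanyl, block or airway device.

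**Working it through.** The plan gives no figure on this point to reproduce. The check is a reading of the text followed by illustrative arithmetic.

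**1. Is anything stated that would be wrong?** No. The two analysis sentences fix the structural model and the estimation method. They neither exclude covariates nor prescribe a faulty covariate step.

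**2. How many choices are open?** A three-compartment model has 3 clearances and 3 volumes, so 6 parameters. Four descriptors are collected, so 6 × 4 = 24 pairs, 6 of them for frailty. The 24 is generous, because weight and height are usually combined.

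**3. Chance findings for frailty, with no true effect.**
- Six independent tests: 1 − 0.95^6 = 26.5% at p<0.05; 1 − 0.99^6 = 5.9% at p<0.01.
- Simulation, with assumed n of 30, 60 and 100, correlations between individual effects of 0, 0.3 and 0.6, and objective-function drops of 3.84 and 6.63 as cut-offs: 19.4–29.5% and 4.7–7.6% over six parameters.
- One prespecified parameter: 5.0–5.9% and 1.0–1.4%.

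A six-parameter search at the stricter cut-off therefore carries about the same risk (5–8%) as one planned test at p<0.05 (5–6%). The simulation treats individual effects as known without error, which is a simplification.

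**4. Frailty standing in for weight.** Assume a 75 kg reference, frail patients d kg lighter, clearance following weight with exponent 0.75, and no frailty effect. The apparent effect is ((75 − d)/75)^0.75 − 1:
- d = 5: −5.0%
- d = 10: −10.2%
- d = 15: −15.4%

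Over exponents 0.5 to 1 the range is −3.4% to −20.0%. Under these assumptions, fitting weight first makes all of these zero.

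**5. Frailty standing in for body composition.** Assume equal weight, reference body fat 28%, frail patients 5 or 10 percentage points higher, and kinetics following fat-free mass. The fat-free ratios are 0.67/0.72 = 0.931 and 0.62/0.72 = 0.861. A weight-scaled model would then show:
- volumes (exponent 1): −6.9% and −13.9%
- clearance (exponent 0.75): −5.3% and −10.6%

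**6. Would a fixed recipe remove this?** One concrete remedy scales on total body weight with exponents 0.75 and 1, tests frailty on elimination clearance only at p<0.01, and refits with fat-free mass as a sensitivity analysis. By step 5, its primary model is the one that can show a spurious −5% to −11% frailty effect on clearance. It also ignores age, leaves early distribution exploratory although time and dose to loss of consciousness are recorded, and needs a bioimpedance prediction equation that the document does not name.

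**7. The orthopaedic patients.** No PD model is given for anyone, so how this group enters it cannot yet be right or wrong. On data capture, the recorded items also omit BIS values and sampling times, without which the announced modelling could not be done. The lists are plainly not exhaustive, and silence on fentanyl does not show that it goes unrecorded.

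I give no figures for a model with no size term at all, which few analysts would accept as final, or for a PD value pooled over regimens, where both the shift and the orthopaedic share would be invented.

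**The case for a change.** The best case for a change is that it is cheap. A short paragraph would settle the size descriptor, the place of frailty and the treatment of orthopaedic patients, with no new size or frailty data and no effect on care. The document calls itself a statistical analysis plan, and frailty and bioimpedance were presumably collected for a reason. Details of opioid, block and airway may also be hard to recover later if nobody wrote them down.

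Part of this stands. The section is thin, and the eventual report should say which covariates were tried, in what order and by what criterion, and should show how the opioid regimens were handled. Confirming that the orthopaedic details are on the record form is sensible housekeeping.

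The rest does not carry the point. The documents state no frailty objective or test, so an unplanned frailty claim is a possibility, not something the plan sets up. The size and frailty choices can be made at any time before analysis without losing data. The orthopaedic question belongs to the writing of the PD model.

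**Conclusion.** No change to the plan follows. This is detail left to the modeller, in work for which no hypothesis test or error rate is stated, and an analyst using nonlinear mixed effects software would normally fill it sensibly. The possible distortions are moderate and conditional: about −5% to −15% on clearance if size is left out, −5% to −11% if weight is used where fat-free mass governs, and a false frailty inclusion in 19–30% of loose six-parameter searches against 5–8% at p<0.01. These figures rest on assumed weights, body fat, exponents and sample sizes; only the counts of parameters and descriptors come from the documents. The conclusion assumes that size is fitted before frailty, that all covariates tried are reported, that opioid regimen is addressed when the PD model is written, and that the anaesthetic record shows opioid, block and airway. A report that presented a frailty effect as confirmatory, or pooled the regimens without comment, would deserve criticism then.
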